 - f. Pain or discomfort
 - g. Anxiety
 - h. Depressed mood
 - i. Difficulty moving or walking
 - j. Difficulty performing activities of daily living such as dressing or bathing
- 4. Have you used mental health services since the time the patient was admitted?
- 5. What is your overall impression of mental health services (choices ranging from very unhelpful to very helpful)

Subjects will be asked to complete the 1) Critical Care Family Needs Inventory (CCFNI) questionnaire, 2) Hospital Anxiety and Depression Scale (HADS), and 3) Impact of Events Scale Revised (IES-R) questionnaire. (**Appendix**)

Subjects will participate in a 30-minute phone interview with a psychologist. The psychologist will review the subject's responses to the above surveys and ask follow-up questions (**Appendix**). The psychologist will ask how the subject has been coping with any psychological symptoms (i.e. anxiety, depression, post-traumatic stress)

The psychologist will describe different types of interventions for people coping psychological symptoms and assess the subject's interest in pursuing any of them.

We will not begin Part 2 until 10 subjects have completed "Part 1- Post-ICU discharge survey and Interview." We will review survey responses and interview transcripts for the first 10 subjects. Based on responses will determine the type(s) of support interventions that will be offered for subjects in this study. An amendment to the study protocol will be made at this time.

Part 2 - Post-ICU psychological intervention

Subjects with clinically significant psychologist symptoms based on either their survey or interview responses will be invited to participate in 6-week trauma-focused intervention with a psychologist.

The program will be brief and delivered online to test the acceptability and feasible of the program, and to gather a preliminary estimate of effect size. We will pilot a group-based intervention (n =3-5) online over Zoom and deliver the intervention across six sessions outlined below. Sessions will last 60-75 minutes depending on participant questions and discussion.

Experiential exercises will be drawn from Acceptance and Commitment Therapy, a related contemporary cognitive behavioral treatment (Hayes, Strosahl, & Wilson, 2012). Some commentary of Viktor Frankl's (1985) work on meaning making will be made in group discussion. Activity scheduling worksheets from Martell, Dimijian and Herman-Dunn (2013) will be used for out of session homework.

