We plan two phases for the study. The first phase, sessions 1-3, focus on introducing the model of behavioral activation and guide the participants to identify activities that will be pleasant, meaningful, or offer a sense of accomplishment and mastery. The first session aims to normalize diverse responses to health-related stress and loss by introducing the behavioral model of depression, and the rationale for behavioral activation. In the second session participants then clarify their values, so that they can begin scheduling pleasant and/or meaningful activities in the third session. These activities are tailored based on each participant's individual goals, priorities and values. The second phase, sessions 4-6, aims to reinforce and sustain positive gains made via behavioral activation and pleasant activity scheduling. Session 4 offers suggestions for problem-solving ways to overcome unhelpful avoidance, a transdiagnostic vulnerability that sustains a number of emotional and psychiatric disorders. Session 5 offers suggestions for overcoming rumination including instruction in mindfulness, and attentional techniques that help participants attend to the outcomes and experiences of the pleasant activities they engage in. Session 6 concludes the program, and guides participants to consider plans to maintain commitment to pleasant activities.

Prior to beginning the intervention and at the completion of the intervention, surrogates will complete the 1) Hospital Anxiety and Depression Scale (HADS), and 2) Impact of Events Scale Revised (IES-R) questionnaire.

At the completion of the intervention, subjects will participate in another 30-minute phone interview with a study investigator. The study investigator will review the subject's responses to the above surveys and ask follow-up questions. The study investigator will ask how the subject has been coping with any psychological symptoms (i.e. anxiety, depression, post-traumatic stress).

All interviews will be audio recorded and transcribed. Two members of study staff will review the transcriptions and use thematic content analysis to determine the types of psychological symptoms that are present and the reason(s) they may be present.

Outcomes

Part 1- Post-ICU discharge survey and Interview

- Critical Care Family Needs Inventory (CCFNI) questionnaire, a 14-question instrument with each question scored 1-4
- Hospital Anxiety and Depression Scale (HADS), 14-questions each question scored on 0-3 scale.

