- Impact of Events Scale Revised (IES-R) questionnaire (measure of PTSD symptoms). This instrument contains 22 questions scored on 0-4 scale.

- Qualitative analysis of interview to determine the prevalence and reason(s) for psychological symptoms

Part 2- Post-ICU discharge survey and Interview

- Each subject's post-intervention HADS score relative to pre-intervention HADS score
- Each subject's post-intervention IES-R score relative to pre-intervention IES-R score
- Qualitative analysis of interview to determine the prevalence and reason(s) for psychological symptoms and effectiveness of the intervention.

When analyzing subject responses, we will account for the following variables

- Whether the patient is deceased or not
- Length of time since hospital discharge
- Whether the subject received mental health services on their own or not
- Whether the subject received daily written summaries in the ICU or not

Statistical Analysis

We expect ~100 subjects to meet inclusion criteria. We expect ~70 to complete Part 1 (Post-ICU discharge survey and Interview). We will determine the prevalence of psychological symptoms and opinions on ICU care by reviewing survey responses and interview recordings. We expect ~30 to complete Part 2 (Post-ICU discharge survey and Interview). We compare pre- to post-intervention survey responses for each subject using a paired t-test. Part 2 will be considered a pilot study. We will use the results to plan a future, adequately powered study.

References

Frankl, V. E. (1985). *Man's search for meaning*. Simon and Schuster.

Hayes, S. C., Strosahl, K. D., & Wilson, K. G. (2011). *Acceptance and commitment therapy: The process and practice of mindful change*. Guilford Press.

Martell, C. R., Dimidjian, S., & Herman-Dunn, R. (2013). Behavioral activation for depression: A clinician's guide. Guilford Press.

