- Use the subject's responses to the *whole* interview to suggest possible types of support interventions and gauge the subject's interest (we are expecting about half of the subjects who complete this interview to complete the support intervention)

Thank the participant for their participation. Is there anything else you would like us to know?

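### Part 2 makes no provision to assess or analyse people who start the programme and stop attending, so its effect estimate is at risk of completer bias of unknown size, probably toward benefit

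*Combined protocol and SAP*

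**What the plan says.** The text on Part 2 (Post-ICU psychological intervention) plans a small online group programme and will "deliver the intervention across six sessions outlined below". It has one pre and one post assessment: before starting and "at the completion of the intervention, surrogates will complete" the HADS and the IES-R. No other Part 2 time point or calendar window is given.

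Under Outcomes, the Part 2 measure is a within-person change: "Each subject's post-intervention HADS score relative to pre-intervention HADS score", with a matching entry for the IES-R. Under Statistical Analysis: "We compare pre- to post-intervention survey responses for each subject using a paired t-test".

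Numbers are given only for people who finish. Statistical Analysis has "We expect ~70 to complete Part 1" and "We expect ~30 to complete Part 2". The interview guide in the Appendix says "we are expecting about half of the subjects who complete this interview to complete the support intervention".

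The documents do not define completion, state how many people are expected to start, say whether those who stop will be surveyed, define an analysis set, or give a missing-data method. Attendance is not among the variables listed for adjustment. Part 2 is called a pilot. Its stated purposes are acceptability, feasibility and a first estimate of effect size, and its results are to be used in planning a later powered study.

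**The concern.** The only post score is tied to completion, and the test needs both scores. Someone who attends two or three sessions and stops may therefore never be asked for a second questionnaire, and would then drop out of the comparison. If stopping is related to lack of benefit or to worse symptoms, the remaining pairs show a larger mean improvement than the starters as a group had.

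At stake is the preliminary effect size, one of the things Part 2 is meant to deliver. If a completers-only change were carried into planning as the effect of starting the programme, the later study could be too small. The feasibility aim is touched as well: without the number who started, a completion rate cannot be reported. The closing interview has the same timing as the post questionnaires, so the reasons for stopping could also be missed.

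**Working it through.** **1. The plan's own numbers.** Half of about 70 is 35, and Statistical Analysis gives about 30 (30/70 = 43%). Both are approximate and I make nothing of the gap. Both count people who finish. No alpha, power, SD, effect size or dropout rate is stated, so the 30 cannot be reproduced from a sample-size formula and reads as a feasibility expectation.

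**2. Size of the bias (assumptions: number of starters, and change in those who stop).** Let c be the share of starters who complete, D the completers' mean change, and rD the mean change in those who stop. Then

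all-starter change = cD + (1 − c)rD, and relative error of the completers' figure = 1/[c + (1 − c)r] − 1.

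For 30 completers of 40 starters, c = 0.75:
- r = 0: 1/0.75 − 1 = 33% too large
- r = 0.5: 1/0.875 − 1 = 14% too large
- r = 1: no error
- r = 1.5: 1/1.125 − 1 = −11%, so too small

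With other assumed numbers of starters:

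| Starters | r = 0 | r = 0.5 | r = 1 | r = 1.5 |
|---|---|---|---|---|
| 35 (c = 0.857) | +17% | +8% | 0% | −7% |
| 40 (c = 0.75) | +33% | +14% | 0% | −11% |
| 45 (c = 0.667) | +50% | +20% | 0% | −14% |

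The sign depends entirely on r, about which the documents say nothing.

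**3. The same on a standardised scale.** Bias = d × (completers' change − change in those who stop), where d = 1 − c. Assume completers improve by 0.5 SD. For d = 10, 20, 30 and 40% (34, 38, 43 and 50 starters for 30 completers):
- no change in those who stop: all-starter effect 0.45, 0.40, 0.35 and 0.30 SD
- equal improvement: 0.50 SD throughout
- improvement of 0.75 SD: 0.525, 0.55, 0.575 and 0.60 SD, so the completers' figure is too low

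**4. Possible effect on planning (only if this change is used directly for sizing, with the same SD in completers and all starters).** For a two-arm comparison at 80% power and two-sided 5% (assumed), n per arm = 2(1.96 + 0.84)²/δ². That gives 63 for 0.5 SD, against 78, 99, 129 and 175 for 0.45, 0.40, 0.35 and 0.30 SD. In the 30-of-40 case, a study sized on the completers' change would have 0.75² = 56% of the required number if r = 0, 0.875² = 77% if r = 0.5, 100% if r = 1, and 1.125² = 127% if r = 1.5.

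**5. Would a likelihood-based model on pre and post scores repair this?** Not by itself. Such a model predicts a missing post score from the pre score, using the relation seen in completers. Take 25% stopping, unrelated to the pre score, with no change in those who stop and 0.5 SD in completers. The true all-starter change is 0.75 × 0.5 = 0.375 SD. The pre means are equal in the two groups, so the model assigns those who stop the completers' mean change and returns 0.50 SD. None of the bias is removed, because the lack of response is never observed.

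**The case against.** The strongest case against is that the text does not actually exclude anyone. A reader might infer that people who stop are certain to be left out, and the documents do not support that. Completion of the intervention can mean the end of the group's course for everyone who began, since session 6 is described as concluding the programme. Aim 3 offers up to six sessions, so partial attendance is foreseen. The outcomes are defined for each subject. The phrase about completing Part 2 is followed by a parenthesis naming the survey and interview, not session attendance. All of this stands: exclusion is the more natural reading, not an established fact. The interview guide, however, speaks of subjects completing the intervention itself. Even on the calendar reading, nothing requires follow-up of those who stop, and the paired test still drops anyone without a post score.

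A reader might also infer that the estimate is definitely biased toward benefit. That is not supported either. The documents give no dropout rate, no reasons for stopping and no outcomes after stopping. People who leave because they feel better would make the bias nil or reverse it. The harmful direction is plausible: the protocol treats avoidance as something that sustains disorders and addresses it only in session 4, and the IES-R counts avoidance as a symptom, so people whose avoidance persists may leave early. That is an argument for probably, not for certainly.

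Finally, it does not follow that the later study will be too small. The plan says the results will inform planning, not that this uncontrolled change will be the sizing input. The pilot label lessens the consequence but does not remove it.

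**Conclusion.** The concern holds as a gap with a risk attached. As written, the Part 2 effect size will most likely rest on completers, because the plan neither provides for assessing people who stop nor says how they are analysed. The resulting bias is probably toward benefit, but its size cannot be determined from the documents. Under the assumption of 30 completers of 40 starters it ranges from a 33% overstatement (no change in those who stop), through 14% (half the change) and zero (equal change), to an 11% understatement (one and a half times the change). Any effect on a later study's size is conditional on that study using this figure. This should be changed before Part 2 data are collected, because post scores that are never requested cannot be recovered by analysis.

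**What to change.** - **Assessment.** Send the HADS and IES-R at the calendar end of each group's six-session schedule to everyone who attended session 1, whatever their attendance. This is the main remedy.
- **Analysis set.** Name all starters (attended session 1) as the main set and keep everyone with a post score in the paired comparison, regardless of sessions attended. Define completion and report completers as a secondary set.
- **Flow.** Report the numbers invited, started, completed and assessed.
- **Missing post scores.** Prespecify sensitivity analyses that include every starter, for example no change from the pre score, set beside the assumption of the same change as those assessed. Read the no-change analysis for its estimate rather than its p-value. Do not rely on a likelihood-based model, which does not remove bias from dropout related to unobserved response.

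The cost is a few lines of protocol and analysis text and reminders to people who have stopped. Some forms will still be missing, and the estimate may be less favourable. The programme itself does not change.

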- 2. To determine the characteristics of ICU care delivery during the COVID-19 pandemic that were associated with the development of psychological symptoms among families.** To achieve this goal, we analyze phone interviews conducted during and after the hospitalization. We compare themes among families who developed psychological symptoms to those who did not.
- 3. To determine whether a trauma-focused cognitive behavioral therapy intervention helps reduce the burden of symptoms among family members with psychological symptoms.** We will pilot a program in which family members with clinically significant psychological symptoms will be offered up to six phone/video counseling sessions with mental health professionals. To determine the effect of this therapy, we will conduct phone interviews and use validated instruments to determine the prevalence of anxiety, depression, and post-traumatic stress disorder after the intervention.

Methods

Enrollment

Surrogates of ICU patients with COVID-19 who were enrolled in the study "ICU Rounding Summaries for Families of Critically Ill Patients" (19042604-IRB01) will be approached to participate in a follow-up study dealing with their mental health after patient discharge. We will email and call surrogates to describe the project and provide an informed consent form for them to review.

Inclusion criteria

- The patient's surrogate was enrolled in "ICU Rounding Summaries for Families of Critically Ill Patients" (19042604-IRB01) and the patient had COVID-19
- The patient has been discharged from the hospital

Exclusion criteria

- None

Intervention

Part 1- Post-ICU discharge survey and Interview

Upon enrollment in this post-ICU discharge follow-up study, the subject (surrogate of the ICU patient) will complete a survey dealing with the patient's course since Rush discharge

1. Is the patient still alive?

- a. If deceased, did the patient pass away at Rush or after discharge from Rush?
- b. If alive, is the patient at home?
 - i. If at home, for how long? Is he/she receiving home health services?
- 2. If the patient did not pass away at Rush, did the patient spend time in a rehabilitation hospital, nursing home, or long-term acute care hospital after discharge from Rush?
- 3. Is the patient currently having any of the following symptoms (check all that apply).
 - a. Fatigue
 - b. Trouble Breathing
 - c. Difficulty speaking
 - d. Difficulty eating
 - e. Difficulty thinking or paying attention

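### Aim 3 and Part 2 promise the effect of the therapy, but one uncontrolled pre-post arm can only estimate change during the therapy

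*Combined protocol and SAP*

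**What the plan says.** Specific Aim 3 is worded causally: "To determine whether a trauma-focused cognitive behavioral therapy intervention helps reduce the burden of symptoms among family members with psychological symptoms". It continues: "To determine the effect of this therapy, we will conduct phone interviews and use validated instruments". The section on the Part 2 intervention lists acceptability and feasibility first, and then adds the goal "to gather a preliminary estimate of effect size".

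The design behind these statements is one arm. Entry depends on symptoms: "Subjects with clinically significant psychologist symptoms based on either their survey or interview responses will be invited to participate". On measurement the plan says: "Prior to beginning the intervention and at the completion of the intervention, surrogates will complete the" HADS and the IES-R. The Statistical Analysis section expects about 70 subjects to complete Part 1 and about 30 to complete Part 2, and gives the analysis in one sentence: "We compare pre- to post-intervention survey responses for each subject using a paired t-test". It calls Part 2 a pilot whose results will help to plan a later, powered study.

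Under Outcomes the plan adds: "When analyzing subject responses, we will account for the following variables". The four variables are whether the patient died, "Length of time since hospital discharge", use of outside mental health services, and receipt of daily summaries in the ICU. No model is named.

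No waitlist, concurrent comparison or follow-up of symptomatic non-participants is described. The control group mentioned in the Interview Guide belongs to the parent study of written summaries.

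**The concern.** The objective and the design do not match. Everyone in the analysis is treated, over the same interval, so the passage of time and the therapy cannot be told apart. Symptoms after a relative's ICU stay may ease or worsen without treatment. The only symptom data in the background section come from the ICU stay, so the documents cannot say which.

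Two things are at stake. One is the conclusion: read literally, Aim 3 invites the investigators to credit the therapy with the whole change, or to dismiss a therapy that prevented worsening. The other is planning: if the change were used as the between-arm difference for the next study, that study could be too small or needlessly large.

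**Working it through.** **Inputs.** From the documents: one arm, about 30 completers in Part 2 and about 70 in Part 1, online groups of 3 to 5, and HADS and IES-R before and after a 6-week programme. The documents give no alpha, SD, target difference, power or untreated change, so there is no power figure to reproduce. I assume two-sided 0.05 and show a range of untreated change.

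**1. What is estimated.** Write each subject's improvement as D = t + u + error, where t is the therapy effect and u the untreated change over the same weeks. The paired t-test estimates mean(t) + mean(u). No subject supplies u alone.

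**2. Whether the covariates help.** Regress D on the four variables, each centred at its mean. The least-squares intercept then equals the raw mean of D exactly. Covariates can show who changes more; they cannot remove u from the mean when nobody is untreated. The interviews also cover treated subjects only.

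**3. The pilot with an inert therapy.** For n = 30, the critical value is t(0.975, 29 df) = 2.045 and the noncentrality is δ√30, with δ in SDs of the change score.

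| Untreated fall δ | Noncentrality | P(p < 0.05) |
|---|---|---|
| 0 | 0 | 5% |
| 0.3 | 1.64 | 36% |
| 0.5 | 2.74 | 75% |

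The 95% CI half-width is 2.045/√30 = 0.37 SD of change. That precision applies to t + u, not to t.

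**4. Planning the next study.** Here the unit is the raw-score SD, which equals the SD of change only when the within-person correlation is 0.5. Suppose the pilot shows a fall of 0.5 SD. A two-sample t-test with 80% power then needs 64 per arm. The therapy part is 0.5 − u.

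| Untreated part u | Therapy part | Needed per arm | Power of 64 per arm |
|---|---|---|---|
| −0.2 (worsening) | 0.7 | 34 | 98% |
| 0 | 0.5 | 64 | 80% |
| 0.1 | 0.4 | 100 | 61% |
| 0.2 | 0.3 | 176 | 39% |
| 0.3 | 0.2 | 394 | 20% |

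**5. Regression to the mean.** If the score before session 1 is a new administration, the selection contributes about zero, provided Part 1 scores correlate equally with the pre and post scores. If the Part 1 score were reused as the pre score, the artefact in SD units would be (1 − r)·φ(z)/q. Assume that the top q = 30/70 = 43% are selected. Then r = 0.5, 0.7 and 0.9 give 0.46, 0.27 and 0.09.

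**6. What else the pilot can pass on.** For normal data at n = 30, the 95% limits for an SD are √(29/χ²) = 0.80 and 1.34 times the estimate. Sample size goes with the square, so the limits there are 0.63 and 1.81. Groups of 3 to 5 also mean only about 30/5 = 6 to 30/3 = 10 therapy groups, while the paired t-test treats subjects as independent.

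**The case against.** The strongest defence is that this is a labelled pilot. The outcomes are stated neutrally, as post-intervention scores relative to pre-intervention scores. Acceptability and feasibility come first, the effect size is called preliminary, and a later powered study is foreseen. No alpha, success rule or go/no-go decision depends on p < 0.05, and the plan does not say how the results will enter the planning. The listed variables include outside services and time since discharge, and Aim 3 relies on interviews as well as on scores.

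Much of this stands. The paired t-test sentence contains no error; the fault lies in the wording of Aim 3 and of the effect-size goal. The 36% and 75% are not error rates of any decision in the plan, and the planning table shows a possible use, not a stated one. What does not stand is that the label, the covariates or the interviews cure the mismatch. The label lowers the weight placed on the result, not the limit on what it measures, and no sentence tells the reader that the change is uncontrolled.

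A reader might also infer that selecting symptomatic subjects guarantees a spurious improvement. The Part 2 text most naturally reads as a fresh administration before session 1, and on that reading the artefact is about zero.

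**Conclusion.** The concern holds as a mismatch between objective and design, of minor to moderate weight. Part 2 can estimate mean change among participants. It cannot estimate the effect of the therapy, and the text promises that it will.

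That conclusion needs no assumed number; it follows from the single arm. The sizes shown do rest on assumptions: two-sided 0.05, independent subjects, normal scores, and an untreated change that the documents do not supply.

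Two stronger readings should be resisted. One is that the pilot will overstate the therapy; without natural-course data, untreated worsening could equally hide a benefit. The other is that the next study will be underpowered; that follows only if the change is taken at face value and part of it is untreated improvement, and the plan commits to neither.

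**What to change.** 1. **Objectives.** In Aim 3, replace determining the effect of the therapy with describing the pre-to-post change in symptoms among family members who take part. In the Part 2 text, replace the effect-size goal with a preliminary, uncontrolled estimate of pre-to-post change.
2. **Statistical Analysis.** The paired t-test can stay. Suggested addition: *Mean change in HADS and IES-R will be reported with a 95% CI as uncontrolled within-subject change. It includes any change that would have occurred without the intervention and is not an estimate of the effect of the intervention.* Allow for the therapy groups in the CI, for example with a group random effect, or state that the CI ignores grouping.
3. **Planning.** Do not take the change at face value as the between-arm difference. Show sample sizes over a range of untreated change, and carry the SD and within-person correlation forward with their uncertainty, not as fixed values.
4. **Baseline.** State that the pre score is the HADS and IES-R completed before session 1. Also report the participants' change from Part 1 to that score as a descriptive interval before the intervention. Note that it includes regression to the mean from symptom selection, follows the Part 1 psychologist interview, and may differ in length between subjects.

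**Cost.** The pilot gives up its efficacy wording and a single planning effect size. The CI may be slightly wider and there is a little more analysis. No new visits or questionnaires are needed.
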